The KITE study is a randomized, controlled and comparative study conducted in collaboration between Child and Adolescent Psychiatry (BUP) Division in Stockholm and Center of Neurodevelopmental Disorders at Karolinska Institutet (KIND). The study protocol was approved by Ethical Review Board in Stockholm (Dnr.2013/739-31, amendment: Dnr.2013/1729-32). The trial is registered with ClinicalTrials.gov (NCT01841151).

Eligibility and Recruitment

Participants are recruited by referrals from Child Psychiatric Clinics, ADHD-center (Habilitering & Hälsa) and children clinics (Barn- och ungdomsmedicinska mottagningar) in Stockholm County. Self-referrals are also welcome. Parents or legal guardian comes to an information meeting that is held at BUP-KIND. Before entering the study, written consent is obtained from the parent or legal guardian of the participant, and verbal assent for children under 13 or written assent for children 13 years and older. Evaluation about inclusion and exclusion criteria's is made after signed informed consent forms arrives with most recent report of neuropsychiatric evaluation confirming the ADHD diagnose.

A total of n=200 children and adolescents with AD/HD between 9-17 years of age will participate in the study alongside with treatment as usual (TAU) such as drug treatment. The duration for the participant in the study is about 30 weeks a total of; (a) baseline testing, (b) five weeks training/TAU, (c) post testing and (d) six months follow-up testing. Measurements are made with self-, parent- and teacher estimations, psychometric tests and neurophysiological measurements at measure points (a), (c) and (d). Each child and parent or guardian participate in an evaluation session to determine eligibility for the study and to establish a baseline score. To confirm AD/HD diagnosis and to ensure IQ>80 a psychiatric interview is done with parents by Kiddie Schedule for Affective Disorders and Schizophrenia for children of 6-18 years (K-SADS)²² and the participant are tested by Vocabulary and Block Design-tests from WISC IV or WAIS IV from where IQ estimate is calculated.

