After referral or self-referral and initial evaluation based on requisitioned report on previously made assessment to establish AD/HD diagnoses the study participants are randomized to four different groups N=50 in each. Two groups of NF (SCP and Ft), WMt group, and the fourth, control group will be measured during treatment as usual (TAU) and will be able to train with self-preferred method after the last measure point. The duration of KITE study is 36 months. After initial screening the duration for participants in the study is approximately 30 weeks a total of; (a) baseline testing, (b) 5 weeks of CLT/TAU, (c) post testing and (d) six months follow-up testing. All the participants attend the study in parallel with TAU, such as drug treatment.

Inclusion criteria

Clinical diagnosis of AD/HD according to DSM-IV-TR and the K-SADS interview, drug naive or under stable medication with stimulants or equivalent for at least 1 month.

Exclusion criteria

IQ <80 (WISC-IV or WAIS-IV), clinically unstable psychiatric condition such as suffering from acute depression, bipolar disorder, severe obsessive compulsive disorder, clinically judged severe self-harming behavior, severe somatic (neurological) disease, or has a very limited knowledge of the Swedish language.

Interventions

Subjects randomized to the training groups, i.e. NF1, NF2 and WMt, comes to the clinic five times per week for five weeks, 25 sessions in total. Each session lasts about 50 minutes.

Two NF methods

NF 1: Slow cortical potential (SCP)

SCP is slower bioelectrical activity in the brain, it is a form of event related potentials (ERPs) and locked in time. It is related to phasic regulation of cortical excitability and apical dendrites of pyramidal cells are believed to be the source of the activity. SCP is characterized of negative and positive shifts lasting from 350(?) milliseconds to several seconds. The negative shift is believed to reflect brain state of allocating attentional resources and increased cortical excitability, and positive shifts reflects inhibition, reduced excitability. In this

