We expect that participants receiving NCT will exhibit improved core ADHD symptomatology and secondary and exploratory outcomes compared with waiting list controls. Moreover, we hypothesize differing effects of Cognitive training in ADHD type of NCT (SCP, Lzs, WMt) based on the participant characteristics (e.g. genetic predisposition, age, IQ, gender, verbal skills, and comorbidity) will predict patterns of treatment effects on the various outcomes. The sample size calculation refers to the three primary outcome endpoints: change in Conners 3 total scores and subscales for parent, self-report, and blind teacher ratings between baseline and follow-up assessment, in the Intention to Treat (ITT) sample. MANOVA for repeated measures (three measurement points, withinbetween subjects' interactions, posthoc tests) will be used for the statistical analysis for the RCT study. Based on available evidence about NCT efficacy medium effects for the primary outcomes are expected. With N=200 (n=50 SCP vs. n=50 Lzs vs. n=50 WMtr vs. n=50 TAU only controls) and alpha=5%, the power (1-beta) is >99% for medium effects (G Power 3.1.7). All data provided for the participants will be included in the analyses. Data will be tested for normality and homogeneity of variance. To verify that the treatment group and control groups are comparable for continuous and categorical demographic variables at pretreatment, a series of independent-samples t-tests and chi-square tests will be conducted. As for primary outcomes, analyses for secondary outcomes will be conducted according to ITT principles. To analyse for the significance of potential factors predicting outcomes (age, IQ, language abilities, gender, comorbidity, genetic variants) in the active NCTs training groups, these are analysed using a logistic regression to explain dichotomized (by median-split) Conners 3 outcomes as the dependent variable.

Adverse events

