Potential adverse events will be continuously monitored with Paediatric side effect checklist (P-SEC⁴³). P-SEC is commonly used in monitoring possible side effects of stimulants. Before training and every 5th training session the parents are interviewed or asked to fill in the P-SEC. For every participant in the active groups are a total of six P-SEC followed through. For the control group P-SEC is rated at pre- and post-measure points and once during the active groups training period. Spontaneous remarks of possible adverse events are thoroughly noted in participant's journals. As the study is conducted within newly established research child psychiatric out-door unit the participants are protected through patient insurance.

Discussion

The project aims to optimize brain functioning to facilitate among other things the ability to focus and maintain attention, controlling impulsive behavior and activity level that are the core difficulties in AD/HD. An important role is also giving access to evaluated non-pharmacological methods with scientific basis to children and adolescents with AD/HD. We know today that untreated AD/HD gives suffering and have far-reaching consequences at the individual, group and society level. There is a need for proven interventions for children and adolescents with AD/HD in addition to drug treatment (SBU, 2012⁴⁴). Some do not respond or respond only marginally to drug treatment, others do not want medications that have side effects and that the core problems

remain after the medical treatment has ceased. CTL are non-invasive methods where NF has shown good preliminary evidence in several international studies in reducing the core symptoms of AD/HD in children and in contrast to psychopharmacological treatment the effect seem to persist foremost of NF training. The study is the first of its kind in Sweden and will be conducted in naturalistic clinical environment that ensures external validity to the study results. If the results show effectiveness CLT methods could broaden the range of treatment for children and adolescents with AD/HD in Sweden. In the long term it can lead to decreased suffering, increased function in everyday life, education and work, and quality of life for the individual patient and their family, and reduced social costs.

Trial status

The first participant enrolled in the study in August 2013.

¹ Polanczyk et al. (2007). Am J Psychiatry, 164, 942-948

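### In the training arms the P-SEC follows session count, so none is specified when a child stops training early, either at stopping or at the post-measure point

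*Combined protocol and SAP*

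**What the plan says.** The Adverse events section of the combined protocol and SAP opens with a broad aim: "Potential adverse events will be continuously monitored with Paediatric side effect checklist". It then sets the timing for the three training arms: "Before training and every 5th training session the parents are interviewed or asked to fill in the P-SEC". The total follows: "For every participant in the active groups are a total of six P-SEC followed through". Under Interventions, a child in a training arm "comes to the clinic five times per week for five weeks, 25 sessions in total".

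The control arm has a different schedule: "For the control group P-SEC is rated at pre- and post-measure points and once during the active groups training period". For all participants there is one unstructured source: "Spontaneous remarks of possible adverse events are thoroughly noted in participant's journals".

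The Measures section does not list the P-SEC among the assessments made at baseline, post-test and six-month follow-up. The documents describe no P-SEC at an early stop and no P-SEC schedule after one. They give no procedure for children who stop training.

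**The concern.** In the training arms, what prompts a rating after baseline is a session attended. Once a child stops attending, nothing in the text prompts another. A side effect that starts between two rated sessions and leads the family to stop is therefore one that the checklist can miss. Ratings lost in this way are not lost at random, because poor tolerability may be the reason for the stop.

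Two things are at stake. First, a child who stopped because of a side effect has no structured check specified afterwards. Second, tolerability bears on the trial's own questions: Aims and objectives asks whether the methods differ and whether they are feasible in clinical settings. The Background presents few side effects as a feature of neurofeedback and mentions fatigue only after the initial training. If such an effect came early enough to cause a stop before session 5, no on-training rating would record it.

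**Working it through.** **Inputs.** From Interventions: 5 sessions per week for 5 weeks. From Adverse events: one P-SEC before training and one at every fifth session, six in total; controls are rated three times, by time point. From Statistical analysis: 50 children per arm, so 3 × 50 = 150 in training arms. The documents give no stopping rate and no interval from onset of a side effect to stopping. Everything from step 3 on rests on stated assumptions.

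**1. The plan's figure.** Sessions: 5 × 5 = 25. On-training ratings: 25 / 5 = 5, at sessions 5, 10, 15, 20 and 25. With the pre-training rating: 1 + 5 = 6. This reproduces the stated total exactly, so none of the six is left for a stopping contact, the post-measure point or follow-up.

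**2. Ratings received by a child whose last session is s.** The number is 1 + floor(s/5). For s = 3, 8, 13, 18 and 23 it is 1, 2, 3, 4 and 5. It reaches six only at s = 25.

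**3. Unrated sessions before a stop.** Assume the last session is equally likely to be any of 1 to 24, and that a rating covers the session at which it is taken. The number of sessions since the last rating is the remainder of s/5.
- The remainder is zero only for s = 5, 10, 15 and 20. So 24 − 4 = 20 of 24 stops (83%) follow at least one unrated session.
- Among those 20, the average is (1 + 2 + 3 + 4)/4 = 2.5 unrated sessions.
- Stops at s = 1 to 4 have no on-training rating: 4/24 = 17%.
- If instead the chance of stopping is constant per session, at 0.5% to 5%, the two shares are 83–84% and 18–26%.

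**4. Is the side effect behind the stop itself unrated?** Let it begin L sessions before the last session attended. Onset cannot precede session 1, so the last session runs from L + 1 to 24, which gives 24 − L equally weighted cases. A case is missed if no multiple of 5 lies between onset and last session, both included. For L = 0 to 4, the number missed is 20 − 5L.

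| L (sessions) | Missed / cases | Share unrated |
|---|---|---|
| 0 | 20/24 | 83% |
| 1 | 15/23 | 65% |
| 2 | 10/22 | 45% |
| 3 | 5/21 | 24% |
| 4 | 0/20 | 0% |

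**5. Illustrative counts.** If 5%, 10% or 20% of the 150 stopped early (assumed rates), 7.5, 15 or 30 children would stop. Multiplying by 20/24 gives about 6, 12 to 13, or 25 who stop after at least one unrated session. These are stops for any reason, not only for side effects.

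**The case against.** A reader might infer that a child who stops training drops out of safety monitoring. The documents do not say that. Spontaneous remarks are noted in journals without any tie to sessions. Stopping training is not leaving the trial: Statistical analysis follows intention to treat, and assessments are planned at post-test and six months. With clinic attendance five times a week, staff may also hear of a complaint before the child stops. This stands, and it limits the point to the structured checklist. Remarks still depend on someone volunteering them, so they do not replace it.

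It can also be said that the text is merely silent. The P-SEC is a parent interview or form and does not need the child to attend. Five sessions a week make the schedule nominally weekly, and six ratings for every active participant may express an intent to obtain all six. That reading is possible, but the text neither ties the ratings to the calendar nor says how the remaining ones would be obtained after a stop.

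Nor should a reader infer that training will look better tolerated than control. The training arms are rated six times and controls three, and more frequent questioning tends to find more events, which works against the loss described here. Control families who withdraw from the study would miss ratings too. The net direction against control is not established.

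Finally, nothing restricts side-effect reporting to children who reached session 5 or later. The Statistical analysis section points the other way: "All data provided for the participants will be included in the analyses". That sentence covers data that were collected; it does not create a rating that was never scheduled.

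**Conclusion.** The point holds as a gap in the structured safety schedule. For a child in a training arm who stops early, the plan specifies no P-SEC at stopping or at the post-measure point, and the stated six ratings are then not delivered. Side effects that lead to a stop can go unrated in these arms, whereas the control schedule does not depend on attendance.

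That 83% of evenly spread stops follow some unrated session depends little on the assumed stopping pattern. Whether the causal event itself is missed depends almost wholly on the onset-to-stop lag. A reader might infer that such events are usually missed. That is so for lags of 0 or 1 session, not for 2 or 3, and at 4 sessions none is missed. With no lag or stopping rate in the documents, the number of children affected cannot be stated. This is a cheap improvement to safety recording and to the tolerability comparison. It does not show that the trial's side-effect results would be biased in a known direction.

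**What to change.** In Adverse events:
- Keep the every-fifth-session ratings for children still in training, so that ratings stay aligned with exposure.
- Add one P-SEC when a child stops training early, by telephone if needed, and record the reason for stopping.
- Rate the P-SEC at the post-measure point for those children, as is already done for controls.

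Where parents respond, the rating at stopping reduces the share of stops with unrated sessions from 20/24 to 0. The cost is a few lines of protocol text and one or two extra parent checklists per child who stops early. Children who complete training get no additional ratings. Some parents of children who stop will not respond, so the gap will narrow rather than close.

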Cognitive learning and training (CLT) methods like neurofeedback (NF) and working memory training (WMt) are non-invasive methods which during the recent years experienced a growing empirical support for improving AD/HD symptoms⁸. NF trains the brains electrical activity through an operant/classical learning paradigm and is supposed to enhance the brains self-regulating ability, i.e. flexibly adapt brain activity to better meet the changing demands of the environment. Previous controlled studies and studies with pre-and post-design has found good results mostly by improving impulsivity and inattention^{9,10,11}. NF has also been demonstrated to induce neuroplastic changes after one session¹² and voluntary control over intrahemispheric functions like the dopamine system¹³. Effects tend to persist after treatment with few side effects (fatigue only after initial training)^{14,15}. WMt focuses on improving working memory functions through challenging exercises in computerized software. Besides encouraging results in enhancing the capacity of foremost visual working memory there has been more sparse evidence that WMt could have beneficial effects on behavioral measures for children with AD/HD^{16,17,18} and questions remain of the nature of the effects and long term effects¹⁹.

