Guidelines recommend multimodal treatment combining psychosocial and educational interventions with medication. Compared with psychopharmacological treatment studies there are quite a limited number of studies on alternative treatments for children and adolescents with AD/HD²⁰. CLT's are non-invasive methods and above all NF has shown good preliminary evidence in several international studies in reducing the core symptoms of AD/HD in children, and has encouraging results in contrast to psychopharmacological treatment that the positive effect persists²¹. WMt has promising evidence of improving working memory capacity and that the good effects also can generalize into other functions but there are a clear shortage of studies comparing WMt with other active interventions and controls (Melby-Lervåg, 2012). If the results would be positive then CLT's could broaden the range of treatment for children and adolescents with AD/HD in Sweden. To date there are several different kinds of neurofeedback training options and two mainstream methods are Slow Cortical Potential training (SCPt) and frequency training (Ft) whereas the latter offers more commercially available options. For the clinical validity of this rather extensive training it is of major importance that potential improvements also last. There is a lack of follow-up studies concerning CLTs (Hodgson et al, 2012, Lofthouse et al, 2012, Melby-Lervåg et al, 2012) and the aim of this sub study is to measure long term outcome from CLT methods

Aims and objectives

Primary aim of the study is to evaluate if neurocognitive training improves core symptoms in AD/HD. Key objectives are (i) are there differences in outcome between the different neurocognitive methods, (ii) can we find predictors that differentiate learners from non-learners, (iii) are neurocognitive methods feasible in clinical settings. Additional important research questions are a) if possible improvements generalize to other settings like

school and home environment, b) does effects last six months after training, c) does the training affect the bioelectrical communication in the brain, d) are there more generalized beneficial outcomes as in perceived quality of life, stress in parents, sleep patterns.

Method/design

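### Scheduled side-effect rating stops at the end of training, so side effects that persist or appear later cannot be compared with controls by structured rating at six months

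*Combined protocol and SAP*

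**What the plan says.** The Interventions section says that each child in a training arm "comes to the clinic five times per week for five weeks, 25 sessions in total". The Adverse events section sets the checklist schedule for these arms: "Before training and every 5th training session the parents are interviewed or asked to fill in the P-SEC". It then fixes the count: "For every participant in the active groups are a total of six P-SEC followed through". For the fourth arm: "For the control group P-SEC is rated at pre- and post-measure points and once during the active groups training period". The only other capture of adverse events is unsolicited: "Spontaneous remarks of possible adverse events are thoroughly noted in participant's journals". That sentence gives no schedule and no end date. The Statistical analysis section names no analysis of adverse events.

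Benefit is followed for longer. The sample-size text in the Statistical analysis section defines the primary endpoints as change in Conners 3 scores by parent, self and "blind teacher ratings between baseline and follow-up assessment, in the Intention to Treat (ITT) sample". Aims and objectives lists, among the additional research questions, "does effects last six months after training". Eligibility and Recruitment puts self, parent and teacher ratings at baseline (a), post-test (c) and six-month follow-up (d), and gives each child about 30 weeks in the study.

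**The concern.** Benefit and harm are observed over different periods. The Background section expects the effects of neurofeedback to outlast training and expects little harm: "Effects tend to persist after treatment with few side effects (fatigue only after initial training". The Discussion names side effects as a reason why some families do not want medication, and describes the effect of neurofeedback as lasting. If wanted changes may outlast training, the plan gives no reason to rule out that unwanted ones may too.

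Under the present schedule, a side effect still rated at session 25 is not followed to resolution by the instrument, and one that begins later is not asked about. At stake is whether the trial can say anything by structured rating, against a concurrent control arm, about side effects after training. The efficacy result does not depend on it.

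**Working it through.** Inputs: 25 sessions in five weeks (Interventions); a P-SEC before training and at every fifth session, six in total, and the control schedule (Adverse events); about 30 weeks per child and the measure points (a), (c) and (d) (Eligibility and Recruitment); training offers after the last measurement (Working memory training; Control).

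1. Reproduce the plan's count. Training arms: 1 + 25/5 = 1 + 5 = 6, at pre-training and sessions 5, 10, 15, 20 and 25. This matches the stated six exactly, so none is left for (c) or (d). Controls: 1 (pre) + 1 (during) + 1 (post) = 3, so none is left for (d).

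2. Set the schedules side by side.

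| Time | P-SEC, training arms | P-SEC, controls | Parent outcome ratings |
|---|---|---|---|
| Baseline (a) / before training | 1 | 1 | yes |
| Five training weeks | 5 | 1 | no |
| Post-test (c) | none listed | 1 | yes |
| Six months (d) | none listed | none listed | yes |

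3. Time without a scheduled P-SEC. On the plan's approximate figures, 30 − 5 = 25 weeks, and 25/30 = 83%. Taking six months as 26 weeks, 26/(5 + 26) = 26/31 = 84%. Both ignore the weeks spent on baseline and post-test, so they are approximate.

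4. Is a controlled comparison still possible at (d)? Yes. The working memory group is offered the second neurofeedback method only after the follow-up measure, and controls are offered neurofeedback only after final data collection. Visit (d) is therefore the last point at which the four randomised arms can be compared before those offers.

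5. After the change. Training arms: 6 + 1 = 7. Controls: 3 + 1 = 4. An optional rating at (c) would make it 8 in the training arms.

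**The case against.** The checklist covers the whole period of exposure to a non-invasive intervention, and the plan's stated expectation is of few side effects, with fatigue only early on. The persistence argument rests mainly on neurofeedback; for working memory training the Background leaves long-term effects open. The aims contain no safety objective. The analysis uses three measurement points, so benefit is not judged at six months alone. All of this is fair. It limits how much weight the gap can bear, but it does not supply a rating at (d).

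A reader might infer that all side-effect monitoring ends with training, or that the trial will hold no information on harm after it. The documents do not support either reading. Spontaneous remarks are recorded with no stated end. The sleep questionnaire is scheduled at follow-up, and the other ratings repeated there could show worsening by arm in symptoms or quality of life. What these sources cannot do is replace the checklist: the remarks are unsolicited and have no planned analysis, and the ratings measure outcomes rather than side effects.

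The missing P-SEC at (c) in the training arms is a lesser matter. Post-test is the next phase after session 25, and no interval between them is stated, so a material gap is not shown.

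A change would also cost more than wording. The study has ethics approval and enrolment began in August 2013, so an amendment may be needed and some children may already have passed (d). This stands and is allowed for in the fix.

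**Conclusion.** The point holds as a cheap improvement. Scheduled P-SEC rating stops at session 25 in the training arms and at post-test in controls, while the primary change runs to six months. About 25 of 30 weeks (83 to 84%) lack a scheduled side-effect rating, so persistence, resolution or late onset cannot be compared with controls by structured rating. This assumes that the schedule in Adverse events is complete; no other section adds a P-SEC.

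No number of affected children is attached, because the documents give no P-SEC rates. Nor would a clean count at six months be a realistic benchmark. The P-SEC is, on the plan's own account, a common tool for stimulant side effects, and drug treatment continues alongside the study, so some background ratings are to be expected. The useful quantity is the difference from controls.

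A reader might also infer that the plan promises a long-term comparison of harm with medication. It does not: the Discussion mentions medication's side effects as motivation and announces no such conclusion.

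**What to change.** - Add the P-SEC at the existing six-month visit (d) in all four arms, completed before controls and the working memory group are offered neurofeedback.
- State in the Statistical analysis section that change from the pre-training rating will be reported by arm against controls, including whether items rated worse at the last on-training rating have resolved by (d).
- For children already past (d) when the change takes effect, limit side-effect conclusions to the training period.
- Reconcile the opening of Adverse events, which describes P-SEC monitoring as continuous, with a schedule that has an end.
- Optionally, add a P-SEC at (c) in the training arms, to give a common end-of-training time point with controls.

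The cost is one more parent checklist per family at a visit where parent ratings are already collected (two per family in the training arms if the rating at (c) is added), plus a protocol amendment. Treatment, randomisation and the efficacy endpoints do not change.

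### Does rating side effects five times after baseline in the training arms but only twice in controls call for a change to the plan?

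*Combined protocol and SAP*

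**What the plan says.** The protocol describes P-SEC under Adverse events as a tool for monitoring possible side effects. For the training arms: "Before training and every 5th training session the parents are interviewed or asked to fill in the P-SEC", and "For every participant in the active groups are a total of six P-SEC followed through". For the controls: "For the control group P-SEC is rated at pre- and post-measure points and once during the active groups training period". Unprompted remarks about possible adverse events are also to be noted in the child's records.

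Under Interventions, a trained child "comes to the clinic five times per week for five weeks, 25 sessions in total". Eligibility and Recruitment sets out the course after baseline testing as "b) five weeks training/TAU, (c) post testing and (d) six months follow-up testing", so post testing is listed as a step separate from training. The Statistical analysis section gives the arms as "n=50 SCP vs. n=50 Lzs vs. n=50 WMtr vs. n=50 TAU only controls". It contains no analysis of P-SEC or of adverse events, and P-SEC is not listed among the primary or secondary outcome measures. The protocol does not restate a recall period for the checklist.

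**The concern.** Trained children have five chances after baseline to have a complaint recorded, and controls have two. The control mid-period rating is tied to no particular week. The training-arm total of six is used up by session 25, so none is expressly assigned to the post-testing visit. No post-baseline occasion is therefore named as common to training and control.

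P-SEC is the plan's only scheduled side-effect instrument, and rating controls is useful mainly as a background rate. The share of children with any complaint is a simple and natural summary, and it is the one that depends on the number of ratings. Harmless training could then look harmful. If each rating instead reaches back to the one before, a per-rating summary would have the opposite fault and make training look safer than it is.

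**Working it through.** **Count of ratings.** Sessions: 5 per week × 5 weeks = 25. Training arms: 1 before training + 25/5 = 6, which reproduces the stated six; 5 fall after baseline. Controls: pre + one mid-period + post = 3; 2 fall after baseline. The post-baseline ratio is 5/2 = 2.5.

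**Ever-reported share, no true difference.** Assume that each rating covers an equal short period and has the same chance q of a complaint. The documents give no q, so a range is shown. With independent ratings the share is 1 − (1 − q)^k, with k = 5 or 2:

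| q | Training (k = 5) | Control (k = 2) | Ratio |
|---|---|---|---|
| 0.05 | 0.226 | 0.098 | 2.32 |
| 0.10 | 0.410 | 0.190 | 2.16 |
| 0.20 | 0.672 | 0.360 | 1.87 |
| 0.30 | 0.832 | 0.510 | 1.63 |

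**Correlated ratings.** Repeated parent reports on one child are unlikely to be independent. In a beta-binomial model with within-child correlation ρ, put s = (1 − ρ)/ρ and b = (1 − q)s. The share is then 1 − ∏(b + i)/(s + i), for i = 0 to k − 1. The last two columns give the chance of a false positive if someone ran a two-sided 5% two-proportion z-test (exact binomial sum) on these shares, at q = 0.10:

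| ρ | Training | Control | Ratio | 50 v 50 | 150 v 50 |
|---|---|---|---|---|---|
| 0 | 0.410 | 0.190 | 2.16 | 68% | 84% |
| 0.3 | 0.271 | 0.163 | 1.66 | 26% | 33% |
| 0.6 | 0.185 | 0.136 | 1.36 | 11% | 10% |
| 0.9 | 0.119 | 0.109 | 1.09 | 6% | 5% |

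As ρ approaches 1 the ratio tends to 1.0. With Fisher's exact test, 50 v 50, the rates at ρ = 0.3, 0.6 and 0.9 are 19%, 6% and 2%. The figure thus depends on an assumed test as well as an assumed correlation.

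**Recall back to the last rating.** Take a weekly risk of 0.10, perfect recall and the control post rating at week 5. Both arms then cover the same five weeks: 1 − 0.9^5 = 0.410 in each, ratio 1.0. Per-rating figures now differ. Training has 0.10. Controls with a mid-period rating at week 2 or 3 average 1 − 0.9² = 0.190 and 1 − 0.9³ = 0.271, which is 0.230, ratio 0.10/0.230 = 0.43. With the mid-period rating at week 1 or 4 they average 0.10 and 1 − 0.9⁴ = 0.344, which is 0.222, ratio 0.45. The bias has changed direction.

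**Matched occasions.** With equal short recall and two post-baseline ratings used in each arm, the expected difference is 0. The false-positive rate is 4.4% to 5.7% over q = 0.05 to 0.30 and ρ = 0 to 0.9.

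**Can occasions be matched from the planned data?** The rating before training and the control pre rating both serve as baseline. At five sessions a week, every fifth session gives a rating about once a week, so a control rating at any point in the training period should fall within days of a training-arm rating if sessions keep to schedule. Session 25 ends the fifth week and probably lies close to post testing. Three matched occasions can be picked from dated forms without collecting anything more.

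**The case for a change.** The best argument for a change is that it would cost almost nothing. A fixed control week, a stated recall period and one reporting sentence need no added forms. Without them, the choice of summary would be made after the data are seen. Collecting P-SEC in controls also suggests that someone will compare the arms, and the any-complaint share is an easy summary to choose.

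The count of 5 v 2 stands, and so does the arithmetic under its assumptions. It is also true that no common post-baseline occasion is named. What does not stand is the step from there to a faulty plan. Harm needs a cumulative summary, a training v control reading of it, and an analyst who overlooks a schedule set out in adjacent sentences. The plan calls for none of these. The recall period decides between a ratio of 1.0 and one near 2.3, and it may belong to the published checklist that the protocol cites; the documents cannot settle that. The most alarming rates, 68% and 84%, require repeated reports on the same child to be independent.

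Writing down a rule would not remove every difficulty either. Restricting cumulative comparisons to common occasions leaves short-lived early effects only described, and the Background reports "few side effects (fatigue only after initial training"). Using all ratings without allowing for week would expose the comparison to any time trend shared by the arms. Since enrolment began in August 2013, controls already seen may have been rated at differing weeks.

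**Conclusion.** No change to the plan follows. This is a gap in reporting detail that a competent analyst fills by comparing the arms at baseline, mid-period and the end, and by describing the remaining training-arm ratings within arm. The denser schedule for trained children is a fair choice for monitoring.

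If a cumulative comparison were made without that care, the ever-reported ratio with no true difference would run from 1.0 to about 2.3. That range assumes equal short recall at every rating, the same risk per rating in both arms, a rate of 5% or more, and any correlation from none to complete. With recall back to the last rating, the ever-reported ratio is 1.0 and a per-rating comparison would favour training at about 0.43 to 0.45 (weekly risk 10%). Both size and direction are therefore hypothetical, because the documents give neither rate, correlation nor recall period. Following the plan as written produces no wrong result: no P-SEC test is specified, the efficacy analyses do not use P-SEC, and the three training arms share one schedule.
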